To assess group differences in the number of weeks of abstinence in the follow-up period (Aim-2a), a Poisson regression model was fit with the total number of weeks of self-reported abstinence in the four-week follow-up period as the dependent variable and treatment, site, and treatment by site interaction as independent variables. We conservatively imputed missing values as non-abstinent, thereby including the total ITT sample. We additionally performed a sensitivity analysis for weeks of abstinence by including the weeks preceding the 9th rTMS-treatment visit and immediate post-visit since these two weeks represent the time following the delivery of a total of 16-sessions of rTMS (a similar dose to early rTMS for depression studies). We calculated the relative risk of having a week of abstinence as a measure of the effect size, along with 95% confidence intervals. We used creatinine-corrected urine cannabinoids to verify self-reported abstinence at follow-up weeks 2 and 4, and calculated the proportion that these two methods were concordant.

To evaluate group differences in the number of days of cannabis use (Aim-2b), we utilized a GLMM with the number of days-per-week of cannabis use as the dependent measure. We included participants in the model who had follow-up data (the completer sample; N=51) and given the apparent divergence in days-per-week of cannabis use in the final two-weeks of the follow-up period, we chose to focus our analysis on that period.

Residual normality was assessed for each of the above models using QQ-plots. We included sex in all models to detect a potential effect, but when no significant effects were found, we excluded sex from the subsequent final models. Apart from craving, this was a pilot trial and not powered a priori to detect statistically significant differences; however, statistically significant *p*-values are noted when observed. When reported, a level of $\alpha = 0.05$ was used (two-tailed), and no adjustments for multiple comparisons were made for this preliminary investigation. Effect sizes at each time point were estimated as Cohens d using means and pooled standard deviations. Statistical analyses were conducted using R software (version 4.2.1, GNU project) and SAS version 9.4 (Cary, NC).

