Aim 2: Determine if a course of excitatory rTMS applied to the DLPFC reduces cue-reactivity in reward network structures during a validated fMRI paradigm. We hypothesize that as compared to participants receiving sham rTMS, participants receiving active rTMS will have a reduced percent signal change in BOLD response in reward structures during a validated cue-reactivity fMRI paradigm following their final rTMS session as compared to prior to their first rTMS session.

Exploratory Aim: Determine if participants receiving active rTMS have a higher rate of abstinence following treatment as compared to participants receiving sham rTMS. We hypothesize that participants receiving active rTMS will be more likely to be abstinent over the final two-weeks of the study period than participants receiving sham rTMS. We will define abstinence as no self-reported cannabis use over the final two weeks of the study, and a ratio of four week to two-week creatinine corrected urine THCCOOH of < 0.5 (10-12).

B. BACKGROUND AND SIGNIFICANCE

Cannabis Use Disorder (CUD) is a common and escalating problem in the United States. The prevalence of CUD more than doubled between 2001-2002 and 2012-2013 (1). Coinciding with the high prevalence of CUD, there has been a high demand for treatment. According to SAMHSA, in 2014 over one million individuals sought treatment for CUD(2). In recent years it has become increasingly clear that those desiring to quit cannabis are rarely able to do so on their own and suffer from a clear withdrawal syndrome(13). Currently available treatments have low long-term success rates(14-17). There has subsequently been significant interest in the development of new treatment options for those individuals with CUD who desire to stop using.

Repetitive transcranial magnetic stimulation (rTMS) is a non-invasive brain stimulation technique that is able to alter cortical excitability and is FDA-approved to treat Major Depressive Disorder. Magnetic fields pass unimpeded through the scalp, skull and meninges, and can directly excite cortical areas. High frequency rTMS (greater than 5 pulses per second) increases cortical excitability(18). Single sessions of rTMS induce temporary changes; however, multiple sessions can induce more long-term changes.

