marijuana during the final two study weeks (via Timeline Follow-Back) as well as a ratio of the creatinine corrected UCTs at the four week follow-up visit divided by the creatinine corrected UCT from the two week follow-up of <0.5 (used in (10-12)) should be sufficient to assign abstinence (yes/no) and assess the overall treatment effect. Logistic regression models will be used to assess end of study abstinence proportions across treatment assignments. Primary analysis models will be reported both unadjusted and adjusted for significant clinical covariates (determined as associated with abstinence from the baseline analysis as well as known clinical confounders). All statistical analysis will be conducted using SAS/STAT version 9.4 (SAS Institute Inc. 2015. SAS® 9.4 Statements: Reference, Fourth Edition. Cary, NC: SAS Institute Inc.).

Missing Data and Attrition. Missing data in longitudinal studies can be a problematic feature but can be mitigated through study design considerations. In order to minimize missing data and study attrition, study simplification and enhanced communication between study staff and participants will be emphasized. We will make every effort to prevent attrition (e.g., phone/text visit reminders, participation compensation, reinforcing adherence to the study protocol at each visit). In addition, in keeping with the Intent to Treat Principle, we will make every effort to continue assessments for the entire course of randomized treatment, even among those who fail to adhere to randomized assignment or stop participating in the study assigned intervention.

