compensated at the end of each visit, and thus will receive pro-rated compensation as they complete the study.

There will be no additional compensation for those choosing to receive open label treatment following the experiment.

b. Sources of Materials

Assessments:

Data collection:

Schedule of visits and assessments and Data Collection:

	Assessment domain	Screen	Baseline	Final rTMS Visit	2-week F/U	4-week F/U
Screening and Enrollment Eligibility:						
MINI International Neuropsychiatric Interview (MINI) for the DSM-5 (54): Structured interview to determine DSM-5 based psychiatric conditions.	Psychiatric history	X				
Urine Pregnancy Test (bHCG)	Pregnancy status	X				
Hamilton Rating Scale for Depression 24-Item (HRSD₂₄)(55): Clinician administered measure of depressive symptoms.	Depressive symptoms	X		X	X	X
The Cannabis Use Disorder Identification Test-R (CUDIT-R)(56): Validated measure assessing severity of disordered cannabis use.	Severity of Cannabis Use	X				
Cannabis Cue-Induced Craving (Aim 1): Primary outcome: Change in MCQ score during cannabis cue paradigm. Secondary outcome: Average weekly change in MCQ assessed during each TMS treatment session.						
The Marijuana Craving Questionnaire (MCQ) (57): Validated measure of cannabis craving. Collected before and after each cannabis cue exposure.	Provoked Cannabis Craving		X	X	X	X
Activation of Reward Structures (Aim 2): Primary outcome: Percent signal change in BOLD response during cue-reactivity fMRI paradigm.						
Substance Use Outcomes (Exploratory Aim): Primary outcome: Number of participants who are abstinent by TLFB for the last 2 weeks of the study with a ratio of four-week to two-week creatinine corrected urine THCCOOH of <0.5. The THCCOOH ratio is able to accurately predict no new cannabis use (10-12).						
Secondary outcomes: change in a) creatinine corrected cannabis level (ng/ml) and; b) subjective use measured by TLFB (number of days used per week and number of cannabis use sessions per week).						
Time Line Follow Back (TLFB) (58): Calendar-based instrument designed to assess substance use.	Self-Reported Substance Use	X	X	X	X	X
Urine Drug Test with Creatinine Corrected Cannabis Level (Collected on the 1st, 5th and 10th rTMS visit, and at follow-up visits)	Objective Substance use	X	X	X	X	X

Delayed Discounting Task (67): Participants choose between receiving hypothetical money immediately or more money if they wait longer.	Cognitive Control		X	X		

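### The SAP replaces the Exploratory Aim's urine-confirmed two-week abstinence outcome with self-reported weeks, gives no reason, and states no by-arm analysis of the planned outcome

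*SAP*

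**What the plan says.** The combined protocol describes one abstinence outcome consistently.

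- Specific Aims, Exploratory Aim: "We will define abstinence as no self-reported cannabis use over the final two weeks of the study", together with a urine condition.
- Schedule of visits and assessments, Substance Use Outcomes, where it is the primary outcome of the Exploratory Aim: "Number of participants who are abstinent by TLFB for the last 2 weeks of the study". The same entry makes the urine condition part of the outcome, requiring the week-4 level to be less than half the week-2 level. The secondary outcomes listed there are the creatinine-corrected cannabis level, days used per week and use sessions per week. A count of abstinent weeks is not among them.
- Statistical Analysis: "Logistic regression models will be used to assess end of study abstinence proportions across treatment assignments", reported both unadjusted and adjusted.
- Sample Size Justification: a separate power statement for this outcome, with the caveat that the sample is not meant to settle the question.

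The SAP (Aim-2a) fits a Poisson regression "with the total number of weeks of self-reported abstinence in the four-week follow-up period as the dependent variable", with treatment, site and their interaction as predictors. Missing values count as non-abstinent, so all 72 randomised participants are included. The one sensitivity analysis adds two weeks from around the end of treatment to the count. On urine, the SAP says "We used creatinine-corrected urine cannabinoids to verify self-reported abstinence at follow-up weeks 2 and 4". The one output that it states from this check is the proportion of agreement between the two methods. It also says that, craving apart, the trial was not powered in advance.

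**The concern.** The protocol required a urine result as well as self-report before anyone was called abstinent. The SAP's modelled outcome rests on self-report alone, over a window twice as long and on a different scale. The SAP neither acknowledges nor explains the change. Because it is written in the past tense, a reader cannot tell whether the change came before or after the data were seen.

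Two things are at stake. First, the protocol says this aim is to supply preliminary data for powering a more definitive study. A ratio of self-reported weeks does not estimate the quantity that the protocol set out to supply. Second, without the planned result beside it, a reader cannot judge whether the change of outcome affected the conclusion. The SAP also numbers this analysis Aim-2a, whereas Aim 2 in the protocol is the fMRI aim, so a reader comparing the two documents by aim number will not find the matching plan.

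**Working it through.** **Step 1. The two definitions side by side.**

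| Feature | Combined protocol | SAP, Aim-2a |
|---|---|---|
| Status | Primary outcome of the Exploratory Aim | Aim-2a |
| Type | Yes/no per participant | Count of weeks, 0 to 4 |
| Window | Final two study weeks | Four follow-up weeks |
| Urine | Week-4/week-2 ratio below 0.5 required | Not part of the modelled outcome; concordance reported |
| Model | Logistic regression | Poisson regression |

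The SAP text contains no binary abstinence outcome, no 0.5 ratio rule and no logistic model. The sensitivity analysis lengthens the count and does not restore the protocol outcome. Aim-2b does look at the final two weeks, but as days of use per week in the 51 participants with follow-up data.

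**Step 2. Can one result stand in for the other?** No. Suppose the abstinent participants in one arm were abstinent in follow-up weeks 1 and 2 only, and the same number in the other arm in weeks 3 and 4 only. The week counts would be equal and the rate ratio would be 1. The protocol outcome would be zero in the first arm and could be well above zero in the second. Likewise, someone who reports no use in weeks 3 and 4 but whose urine ratio is 0.5 or more adds two weeks to the SAP count and is non-abstinent under the protocol.

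**Step 3. The protocol's power figure.** Inputs from Sample Size Justification: 36 per group, 10% placebo rate, at least 30% greater with rTMS (read as percentage points, so 40%), 5% type 1 error, 80% power. Sidedness is not stated for this aim; two-sided is assumed, as in the SAP.

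- Fisher's exact test, full enumeration: 80.0%. This matches the stated 80%.
- Normal approximation: z = [d√n − 1.96√(2p̄(1−p̄))] / √(p₁(1−p₁) + p₂(1−p₂)), with d = 0.30, n = 36 and p̄ = 0.25. That is (1.800 − 1.200)/0.574 = 1.04, giving power of 85.2%.

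The stated power therefore belongs to the binary outcome. The documents give no mean, variance or power for the Poisson count.

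**Step 4. Power of the planned outcome with missing counted as non-abstinent.** Assume loss is equal by arm, 10% and 40% hold among participants with data, and all participants without follow-up data lack the outcome.

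- Planned attrition of 25%: 0.10 × 0.75 = 7.5% and 0.40 × 0.75 = 30%. Power is 61% (Fisher) or 69% (normal).
- Observed follow-up, 51 of 72, so 21/72 = 29.2% missing: 0.10 × 0.708 = 7.1% and 0.40 × 0.708 = 28.3%. For the normal approximation, (1.275 − 1.058)/0.519 = 0.42, giving 66%. Fisher gives 58%.
- Expected events in the second case: 36 × 0.0708 ≈ 3 against 36 × 0.2833 ≈ 10.

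**The case against.** The strongest reply is that this is an exploratory outcome in a pilot. Both documents limit what the sample can say about it, and the SAP keeps urine as a check. All of that stands and sets the weight of the point. It does not explain why the planned result is absent from the SAP.

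A reader might infer more than the documents support.

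- *That a primary trial endpoint was switched.* The protocol's main aims are cue-induced craving and fMRI cue reactivity. Abstinence is the primary outcome of the Exploratory Aim only.
- *That the outcome was chosen after seeing the data.* The SAP admits a data-led choice for Aim-2b, where the final two weeks were selected because days of use appeared to diverge then. It says nothing of the kind for Aim-2a.
- *That urine changed no one's classification, or that concordance was not examined by arm.* The SAP is silent on both. Nor can the documents show whether the protocol outcome was analysed elsewhere.
- *That self-report shrinks the treatment ratio by a known amount.* If a share f of everyone non-abstinent reported abstinence, p′ = p + f(1 − p) would take 10% and 40% to 19% and 46% at f = 0.1 (ratio 4.0 to 2.4), and to a ratio of 1.9 at f = 0.2. These values of f have no source in the documents, and the protocol's 10% is a participant-level figure rather than a weekly one. People imputed as non-abstinent also cannot over-report. With 70.8% followed in each arm, and 10% and 40% now taken as rates in all randomised, p′ = p + f(0.708 − p). The ratios become 16.1% against 43.1% (2.7) and 22.2% against 46.2% (2.1). Equal over-report only dilutes the ratio, and nothing in this double-blind sham design shows that it differed by arm.
- *That each self-reported week could be corrected from urine.* Follow-up samples are taken only at weeks 2 and 4. The ratio covers one two-week interval and cannot place use within a week.

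The protocol definition also has a weakness. Someone who stopped early and is already near the assay's lower limit at week 2 may be unable to halve the level by week 4. The documents do not address this. It could justify a change of outcome, but the SAP would have to say so.

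**Conclusion.** The point holds as an unexplained change to an exploratory outcome, with no by-arm analysis of the planned version stated in the SAP. Type, window, urine requirement and model all differ, and Step 2 shows that the two outcomes can give different answers from the same participants. It should be corrected before abstinence results are used to plan a further trial. It does not bear on the craving analysis of Aim 1.

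The size of any bias in the treatment ratio cannot be derived from the documents, and the over-report figures above are an assumed illustration only. What can be given is the precision of the planned analysis: about 58 to 66% power at 10% against 40%, instead of the stated 80%. That range rests on 21 of 72 missing, equal loss by arm, and those rates applying to participants with data. The protocol's placebo range of 5 to 15% was also based on a different definition (urine THCCOOH at or below 50 ng/ml), so 10% is itself uncertain for the ratio-based outcome.

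**What to change.** 1. Report the protocol-defined outcome by arm as the planned exploratory abstinence result: no self-reported use over the final two weeks and a week-4/week-2 creatinine-corrected THCCOOH ratio below 0.5. Include all 72 randomised participants and count missing as non-abstinent, as the SAP already does. Use logistic regression with site, or an exact test if events are as sparse as Step 4 suggests.
2. State that this missing-data rule replaces the last-observation-carried-forward rule in the protocol's section on relapse and drop-out.
3. Label the self-reported week count as changed from protocol, and give the date and reason for the change.
4. Give self-report/urine concordance by arm, with the rule used to call a pair concordant at each of weeks 2 and 4.

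The protocol already schedules the calendar and urine data at both follow-up visits, so the cost is one model and one table. The estimate will be imprecise and should be presented with its confidence interval as preliminary.

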A Preliminary Investigation of Pre-Frontal Repetitive Transcranial Magnetic Stimulation (rTMS) for the Treatment of Cannabis Use Disorder

Statistical Analysis Plan

NCT03144232

June 27, 2023

We calculated descriptive statistics such as means and standard deviations (SD) for all continuous variables and proportions for categorical variables. We compared demographic, screening, blinding, and adverse event variables (compiled using MEDdra criteria) across condition and site using t-tests or the Wilcoxon Rank Sum test for continuous variables and the Chi-Square or Fisher's Exact test for categorical variables.

For Aim-1, we utilized a generalized linear mixed-effects model (GLMM) to perform the analyses, with the full ITT sample (N=72) and the total MCQ-SF score as the dependent measure. We used two types of a priori models for each analysis: 1) a three-way interaction model which included an interaction between treatment, site, and time, as well as the main effects of treatment, site, time, and all pairwise interactions between the main terms, and 2) a two-way interaction model which included treatment, time, an interaction between treatment and time, and site. We considered pre- and post- variables with a strong clinical rationale for inclusion in covariate adjustment including the amount of time since the last cannabis use, CWS score, the days-per-week of cannabis use, the grams of cannabis used per day, and the number of cannabis use sessions per day.

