Statistical Analysis: Baseline demographic and clinical measures will be compared across treatment groups using standard statistical methods (i.e., categorical variables compared using Pearson chi square test of independence; continuous variables compared using univariate ANOVAs). Characteristics that display imbalance at the baseline measure, association with the dependent variable, or are known to be predictive of cue induced craving, reactivity, or cannabis-use outcomes will be assessed for inclusion as covariates in the final models. To test our primary hypothesis that a full course of active excitatory rTMS will reduce cue induced craving as compared to sham rTMS (Aim 1), generalized linear mixed effects models will be constructed to estimate treatment group differences in craving scores. Overall statistical significance for the effects of treatment group, time, and their interaction will be assessed using a likelihood ratio test that compares the final model, to a model consisting of an intercept term alone. The hypothesis that those receiving active rTMS will have decreased craving will be tested using model-based estimates to construct group level comparisons across all the planned time points. Normality of residuals will be tested for these models and when found in error, appropriate transformations or non-parametric methods will be conducted. For Aim 2 (evaluating the impact of rTMS on cannabis CR), BOLD response during the cannabis cue vs. neutral cue trials will be the primary contrast of interest to test hypotheses. Where significant differences are observed, parameter estimates from task-based models, from each ROI will be extracted and relations with clinical endpoints examined. For our exploratory Aim: The primary analysis will involve preliminarily investigating the efficacy of active rTMS, compared to sham rTMS in increasing the proportion of cannabis abstinent participants during the final two weeks of study treatment (four-week follow-up). A combination of self-reported abstinence from

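### Aim-2b analyses days of cannabis use in a two-week window picked because the data diverged there, does not label the result post hoc, and leaves out 21 of the 72 randomised participants

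*SAP*

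**What the plan says.** The Aim-2b paragraph of the SAP fits a generalized linear mixed model (GLMM) to weekly days of cannabis use. On the sample it says "We included participants in the model who had follow-up data (the completer sample; N=51"). On the window it says "given the apparent divergence in days-per-week of cannabis use in the final two-weeks of the follow-up period, we chose to focus our analysis". The closing paragraph of the SAP sets a two-tailed 0.05 level, notes significant p-values where they occur, and adds that "no adjustments for multiple comparisons were made for this preliminary investigation". It also says "Apart from craving, this was a pilot trial and not powered a priori to detect statistically significant differences".

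The protocol's schedule of assessments (section E) lists days of use as a secondary outcome of the Exploratory Aim: "subjective use measured by TLFB (number of days used per week and number of cannabis use sessions per week"). It gives no window. Where the protocol does fix the last two weeks (section A, Exploratory Aim; section D, Statistical Analysis; section E, schedule of assessments), the endpoint is abstinence yes or no, for example "increasing the proportion of cannabis abstinent participants during the final two weeks of study treatment (four-week follow-up").

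On missing data, the protocol section on relapse, drop-out and clinical deterioration prescribes last observation carried forward (LOCF) for every outcome. Aim-1 in the SAP uses all 72 participants. Aim-2a in the SAP says "We conservatively imputed missing values as non-abstinent, thereby including the total ITT sample".

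**The concern.** There are two separate problems.

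**Window.** A test run where a difference has already been seen rejects more often than its nominal 5% when there is no effect, and the estimate from that window is exaggerated on average. Describing the whole trial as preliminary corrects neither. The SAP does not say whether the other follow-up weeks were modelled. Its Aim-1 paragraph describes the models for each analysis as a priori, which could lead a reader to think the Aim-2b analysis was fixed beforehand.

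**Sample.** Having follow-up data is determined after randomisation. If retention depends on cannabis use or on arm, the 51 completers no longer form a randomised comparison. The SAP gives no arm split, no reasons for loss and no sensitivity analysis for this outcome.

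The trial is meant to inform a larger one, so an inflated or biased estimate of days of use could carry over into that design.

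**Working it through.** **Denominator.** The protocol's Sample Size Justification needs 27 per group and allows 25% attrition: 27 / (1 - 0.25) = 36 per group, 72 in total. This reproduces the stated size and matches the SAP's intention-to-treat N of 72. Aim-2b has no sample size or power figure of its own.

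**Left out.** 72 - 51 = 21, and 21/72 = 29.2%. The planned ceiling was 25%, or 18 of 72.

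**Type I error of a selected window.** Assumptions: 26 vs 25 completers (the split is not reported); four weekly normal values with no true effect; a two-sample t-test on window means (49 df); the larger |t| of the candidate windows compared with the 0.05 critical value; 60,000 replicates per setting. The documents give no week-to-week correlation for this outcome, so 0.3 to 0.9 is assumed, as compound symmetry (CS) or AR(1).

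| Candidate windows | Structure | 0.3 | 0.5 | 0.6 | 0.75 | 0.9 |
|---|---|---|---|---|---|---|
| All four weeks, or 3-4 | CS | 7.5% | 7.0% | 6.7% | 6.3% | 5.7% |
| | AR(1) | 8.0% | 7.6% | 7.4% | 6.8% | 6.1% |
| Weeks 1-2, or 3-4 | CS | 9.3% | 8.6% | 8.2% | 7.5% | 6.4% |
| | AR(1) | 9.6% | 9.5% | 9.1% | 8.5% | 7.3% |
| 1-2, 2-3, or 3-4 | CS | 11.3% | 10.2% | 9.4% | 8.3% | 6.8% |
| | AR(1) | 12.2% | 11.3% | 10.6% | 9.4% | 7.8% |

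A window fixed in advance gives 4.9% to 5.1%. At 0.60 to 0.75, the only correlation range in the documents (given for craving), the three sets give 6.3-7.4%, 7.5-9.1% and 8.3-10.6%. Rounding and bounding the values to 0-7 days (40,000 replicates) gives nearly the same: 4.8-5.2% for a fixed window, then 5.5-7.9%, 6.2-9.7% and 6.7-12.1%.

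**Exaggeration.** With a true effect of zero, mean |Cohen's d| is about 0.23 for a fixed window and 0.24 to 0.35 for a selected one.

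**Completer bias.** Take 36 per arm, mA and mS lost in the active and sham arms (mA + mS = 21), and dropouts using δ more days per week than completers. The all-randomised mean in an arm is the completer mean + δ × m/36. The bias in the active-minus-sham contrast (completers minus all randomised) is therefore -δ × (mA - mS)/36.

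- 14 vs 7 lost: -7δ/36 = -0.19, -0.39 and -0.58 for δ = 1, 2 and 3. For 7 vs 14 the signs reverse.
- 10 vs 11 lost: +δ/36 = +0.03, +0.06 and +0.08.
- 10 vs 11 lost, with a 2-day excess in one arm's dropouts only: -2 × 10/36 = -0.56 if active, +2 × 11/36 = +0.61 if sham.

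With no assumption about the missing values beyond the 0-7 scale, the difference in all randomised participants is undetermined over a width of 21 × 7/36 = 4.1 days per week.

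**The case against.** The strongest reply is that nothing was hidden. The reason for the window stands in the same sentence as the analysis, the SAP calls the trial a pilot powered only for craving, and the protocol places days of use under an Exploratory Aim. On that view the fault is a missing label. The disclosure deserves credit, but it does not restore the error rate or supply the four-week and all-randomised results. The SAP itself calls the analysis Aim-2b and never describes it as exploratory.

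Several narrower points stand:

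- That the divergence was between arms is an inference, although the paragraph opens by saying it concerns group differences.
- The documents contain no Aim-2b p-value, and focusing on two weeks does not prove that the others were never modelled.
- The protocol's intention-to-treat statement (Missing Data and Attrition) is mainly a commitment to keep collecting data. Aim-2a's rule suits a yes/no weekly outcome and need not carry over to a 0-7 count. The LOCF sentence is the only direct conflict; the others show an unexplained difference in approach.
- Nothing in the documents suggests a weeks 2-3 window. Without that set, and at correlations of 0.60 to 0.75, the inflation is modest: 6.3% to 9.1%.
- The simulation uses a t-test where the SAP uses a GLMM, and how the divergence was judged is not stated.
- The dropout scenarios show that bias is possible, not that it occurred.

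**Conclusion.** The concern holds and should be fixed. Three facts rest on the documents alone: the window was chosen from the observed outcome, the result carries no post hoc label, and 21 of 72 randomised participants are left out. The protocol's abstinence window is at most partial precedent, because it belongs to a different endpoint and is not the reason the SAP gives.

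The sizes rest on assumptions. The type I error is probably somewhat above 5%, with an illustrated range of 5.7% to 12.2% depending on the candidate windows and the correlation. The size and direction of any completer bias are unknown; the assumed scenarios span -0.58 to +0.61 days per week and include values near zero. For a disclosed secondary outcome in a pilot trial, this limits what Aim-2b can support. It does not touch the craving analysis.

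**What to change.** 1. Make the main Aim-2b analysis a GLMM on weekly days of use from the Timeline Follow-Back in all 72 participants, using every available baseline, on-treatment and follow-up week. Keep the terms of the SAP's second model: "a two-way interaction model which included treatment, time, an interaction between treatment and time, and site". Enter baseline use as the first repeated value, so that participants with no later data still enter.
2. State one contrast. The protocol gives no window for this outcome; the average treatment difference over all four follow-up weeks uses the whole period, as Aim-2a does.
3. The model relies on missing at random. Add a missing-not-at-random sensitivity analysis for those without follow-up, such as return to baseline use, or delta-adjusted imputation over a stated range. A range of 0 to 3 days per week is an example, not a figure from the documents.
4. Report losses by arm with reasons.
5. Report the final-two-week result only as post hoc and exploratory, and the completer result only as a sensitivity analysis.
6. State one missing-data rule for this outcome and reconcile it with the protocol's LOCF sentence.

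The cost is SAP wording, one re-run of the model and one sensitivity analysis, with no new data collection. The documents do not show how much on-treatment data the 21 provided. Any who contribute only a baseline value will add little information on the treatment difference. The main result may look less favourable than the current one.
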